#### Age

The age of a subject is defined as the number of whole calendar years from the subject’s date of birth to the date of informed consent.

#### Baseline Value

For purposes of analysis, the baseline value is defined as the last non-missing value obtained prior to initiation of study medication.

#### Change from Baseline

Change from Baseline for a given endpoint is defined as the value at the analysis visit minus the baseline value.

#### Duration of alopecia

Date of Informed Consent minus the original onset date of alopecia as reported on the History of Alopecia page of the CRF.

#### Duration of current episode of alopecia

Date of Informed Consent minus the onset date of current episode of Alopecia as reported on the History of Alopecia page of the CRF.

#### Prior Medications

Prior medications are those medications taken prior to the initiation of study medication, regardless of whether it continues into the blinded treatment period.

### Concomitant Medications

Concomitant medications are those medications taken on or after the initiation of study medication. This definition includes medications started prior to the initiation of study medication but continuing concomitantly with the study medication.

DLQI Total Score - The scoring of each question is as follows:

Very much=scored 3, A lot=scored 2, A little= scored 1, Not at all= scored 0, Not relevant=scored 0, Question 7, 'prevented work or studying'=scored 3.

The DLQI is calculated by summing the score of each question resulting in a maximum of 30 and a minimum of 0. The higher the score, the more quality of life is impaired.

### Adverse Event

An AE is the development of an undesirable medical condition or the deterioration of a preexisting medical condition following or during exposure to a pharmaceutical product, whether or not considered casually related to the product.

Every new episode or clinically significant worsening of a chronic condition (e.g., headaches, seasonal allergies, depression, or hypertension) should be reported as a separate AE, even if the condition is reported in the subject's medical history. Hair growth in unexpected areas, such as facial hair in women, should be reported as an adverse event

### Treatment-Emergent Adverse Event (TEAE)

Any recorded AE that occurs on or after the initiation of study medication and within 30 days after the date of Visit 9 or after the date of last dose of study medication will be considered treatment-emergent.

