## AMENDMENT HISTORY

Amendment 1.0 (Protocol Version 2.0 dated 20Jul2018): The primary reason for Amendment 1.0, Protocol Version 2.0 dated 20Jul2018 was to decrease the number of subjects enrolled in the study which are sufficient to explore the efficacy and safety in this initial Phase 2 study. In addition, a substudy was added to determine the trough levels of ATI-502 in the blood and pharmacodynamic effects at trough.

Amendment 2.0 (Protocol Version 3.0 dated 19Sep2018): The primary reason for Amendment 2.0, Protocol Version 3.0, dated 19SEP2018 was to add additional safety assessments, specifically – clinical laboratory testing (chemistry and hematology) at Visit 5, Visit 7 and Visit 8 and to remove pharmacodynamic testing in a subset of subjects at Visit 2, Visit 4, Visit 6 and Visit 9.

Amendment 3.0 (Protocol Version 4.0 dated 08Nov2018): The primary reason for Amendment 3.0, Protocol Version 4.0, dated 08NOV2018 is to give subjects the option to initiate treatment with ATI-502 Topical Solution, 0.46% to explore if hair regrowth can be maintained or continued following cessation of treatment with ATI-501 Oral Suspension. Eligible subjects will be given the option at Visit 9 to enter an open-label study ATI-502-AA-203.

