Among patients with AA, patients with higher disease burdens are unlikely to have satisfactory outcomes with current therapies. Aclaris Therapeutics, Inc. is developing ATI-501 as a treatment for stable patchy AA, AU or AT. ATI-501 is an oral prodrug that is rapidly converted presystemically to ATI-502, a potent highly selective inhibitor of Janus kinase 1 (JAK1) and Janus kinase 3 (JAK3). This study will evaluate whether or not the orally administered JAK1/JAK3 inhibitor prodrug, ATI-501, will attenuate both IL-15 and IFN-gamma signaling, thereby blocking re-activation of CD8+NKG2D+ memory T-cells, and aborting the cytotoxic T-cell inflammatory response underlying AA.

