### **3. INVESTIGATIONAL PLAN**

#### **3.1. Overall Study Design**

This Phase 2, multicenter, randomized, double-blind study is designed to evaluate the safety, tolerability and efficacy of ATI-501 Oral Suspension in subjects with AA, AU or AT. Subjects will be required to have a clinical diagnosis of stable AA, AU or AT with 30% to 100% total scalp hair loss for a duration of at least 6 months up to and including 12 years (inclusive). Stable AA, AU or AT is defined as no areas of spontaneous terminal scalp hair growth.

During the screening period, subjects will be assessed for eligibility into the study. Subjects will receive ATI-501 Oral Suspension, 400 mg, 600 mg, or 800 mg or Placebo Oral Suspension twice-daily for up to 24 weeks. Assessment of response to treatment will be performed at Week 4, Week 8, Week 12, Week 16, Week 20, Week 24, and post-treatment Week 28. Safety and tolerability will be evaluated at each study visit by assessment of adverse events, clinical laboratory tests, and vital signs, and at select visits, ECGs.

Subjects who complete study visits through Visit 9 will have the option to roll over into an open-label study ATI-502-AA-203. Subjects who withdraw consent or meet study medication discontinuation criteria (Section 3.4.1.2) on study ATI-501-AUAT-201 will not be eligible for roll-over to study ATI-502-AA-203. Subjects who complete the assessments for Visit 9 and then meet study ATI-502-AA-203 entry criteria and provide written consent will skip post-treatment Visit 10. Subjects who are not eligible for ATI-502-AA-203 or who decline to participate should return for the final Visit 10 assessments.

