### **8.3. Reporting Adverse Events**

#### **8.3.1. Adverse event reporting period**

The investigator must start reporting non-serious AEs from the time of the subject’s first dose of study medication until 30 days after the last dose of study medication. Reporting for SAEs must start when the subject signs the ICF and continue until 30 days past the subject’s last dose of study medication, whether or not they are related to the study.

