#### **Treatment Assignment:**

A total of approximately 95 subjects will be randomized in a 1:1:1:1 ratio:

- Placebo Oral Suspension, twice daily (BID) for 24 weeks (6 months)
- ATI-501 Oral Suspension, 400 mg, BID for 24 weeks (6 months)
- ATI-501 Oral Suspension, 600 mg, BID for 24 weeks (6 months)
- ATI-501 Oral Suspension, 800 mg, BID for 24 weeks (6 months)

During the screening period, subjects will be assessed for eligibility into the study. Subjects will receive ATI-501 Oral Suspension, 400 mg, 600 mg, or 800 mg or Placebo Oral Suspension twice-daily for up to 24 weeks. Assessment of response to treatment will be performed at Week 4 (Visit 4), Week 8 (Visit 5), Week 12 (Visit 6), Week 16 (Visit 7), Week 20 (Visit 8), Week 24 (Visit 9), and post-treatment (Visit 10). Safety and tolerability will be evaluated at each study visit by assessment of adverse events (AEs), clinical lab tests, vital signs, and at select visits, ECGs. The primary analysis will be conducted after all subjects complete Visit 9 or Visit 10.

Subjects who complete Visit 9 (Week 24) will be eligible to enter a 28-week open-label study ATI-502-AA-203. Subjects who decline or are not eligible for ATI-502-AA-203 should be seen for the Visit 10 (Post-treatment) assessments.

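### The TEAE definition has no cut or flag at the first open-label ATI-502 dose, so events starting after roll-over could be counted under the blinded arms

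*SAP*

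**What the plan says.** **The window.** SAP 4.3.6 counts any recorded AE from the start of study medication onward as treatment-emergent, if it falls "within 30 days after the date of Visit 9 or after the date of last dose of study medication". It does not say which date governs when Visit 9 and last dose differ. The only exclusion from the TEAE tables, in SAP 6.3.1, is onset before study medication.

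**Roll-over.** Protocol 3.1 states: "Subjects who complete study visits through Visit 9 will have the option to roll over into an open-label study ATI-502-AA-203". SAP 1.1 agrees: "Subjects who complete Visit 9 (Week 24) will be eligible to enter a 28-week open-label study ATI-502-AA-203". Neither restricts this by arm. Those who "meet study ATI-502-AA-203 entry criteria and provide written consent will skip post-treatment Visit 10".

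**The open-label product.** The Protocol's Amendment History names it as ATI-502 Topical Solution, 0.46%. Protocol 1.2 gives its relation to the study drug: "ATI-501 is an oral prodrug that is rapidly converted presystemically to ATI-502".

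**Recording.** Protocol 8.3.1 sets non-serious AE reporting from the "first dose of study medication until 30 days after the last dose of study medication". Protocol 8.2.1.1 requires AEs within 30 days of stopping treatment to be entered in the eCRF. Neither section makes an exception for roll-over subjects.

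**Attribution.** SAP 5.2 analyses the Safety population by treatment received. SAP section 6 defines treatment groups as the ATI-501 groups and placebo, so there is no open-label category.

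**The concern.** Read together, these rules let an AE that starts on open-label ATI-502 enter the TEAE table under the blinded arm. A placebo subject who rolled over could contribute to the placebo column an event that began on the active moiety. An ATI-501 subject could contribute to an oral-dose column an event that began on a topical product. Subjects who do not roll over are off drug over the same days, so the last 30 days of each arm's window can mix different exposures.

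Safety and tolerability are part of the primary objective. With about 24 subjects per arm, one subject moves an incidence by about 4 percentage points, so even a few such events would show in the tables.

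**Working it through.** The plan states no figure for this point, so there is none to reproduce. The check is a comparison of rules, a day count and an illustration on assumed inputs.

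**1. Can such an event reach the table?** The sections above allow entry to open-label treatment after Visit 9, require recording for 30 days after last dose, exclude only pre-dose onsets, and provide no open-label column. An event recorded here with open-label onset therefore meets the TEAE definition and falls under the blinded arm.

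**2. How long can the overlap be?** The Schedule of Assessments puts Visit 9 on Day 169 (±3) and Visit 10 on Day 197.
- Window end: 169 + 30 = Day 199 (Day 196 to 202 with the visit window).
- Largest overlap, with open-label dosing on the Visit 9 day: 30/199 = 15.1% of the window.
- With an assumed lag of 7, 14 or 28 days to the first open-label dose: 23/199 = 11.6%, 16/199 = 8.0%, 2/199 = 1.0%.

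**3. How much could placebo incidence change?** Assumptions, none from the documents: 30% with at least one TEAE by Day 169 at a constant hazard, hazard doubled on open-label drug, full capture in this study's database, and roll-over unrelated to earlier AEs.
- Daily hazard: h = −ln(0.70)/169 = 0.00211.
- Day 199 at an unchanged hazard: 1 − exp(−199h) = 34.3%.
- Day 199 with the hazard doubled for 30 days: 1 − exp(−(169 + 60)h) = 38.3%.
- Excess due to open-label drug: 38.3 − 34.3 = 4.0 points, at 100% uptake and zero lag.

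The step from 30% to 34.3% is only 30 more days of follow-up at the same hazard. Any 30-day tail would produce it, so it is not contamination.

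**4. Scaling by uptake (zero lag).** Excess = 4.0 × uptake; subjects = 23.75 × excess/100, with 95/4 = 23.75 per arm.

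| Uptake (assumed) | Excess, points | Subjects per arm |
|---|---|---|
| 25% | 1.0 | 0.2 |
| 50% | 2.0 | 0.5 |
| 90% | 3.6 | 0.9 |
| 100% | 4.0 | 1.0 |

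**5. Scaling by lag (100% uptake).** Excess = exp(−199h) × (1 − exp(−h × overlap days)), with exp(−199h) = 0.657. Overlaps of 23, 16 and 2 days give 3.1, 2.2 and 0.3 points.

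**The case against.** **Capture is uncertain. This stands.** The definition covers recorded AEs only. Roll-over subjects skip Visit 10, the only scheduled AE collection after Visit 9, and Protocol 8.3.4 elicits AEs at visits. Their later events may go to the open-label study's database. The 30-day duty in Protocol 8.2.1.1 and 8.3.1 still applies to them, so some events can enter; how many cannot be known from the documents.

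**Timing is not given. This stands.** Roll-over needs the other study's entry criteria and written consent. Nothing says that open-label dosing starts at Visit 9, so 30 days is a ceiling.

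**The hazard is speculative. This stands.** The open-label product is a 0.46% topical solution, against 400 to 800 mg orally twice daily, and its systemic exposure is not stated. The doubling is for illustration only.

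**No formal inference is affected. This stands.** Safety output is descriptive, Protocol Version 5.0 dropped the chi-square test on AE incidence, and all AEs are listed by subject.

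**The Visit 9 anchor is not the cause. This stands.** Dosing runs 24 weeks, so last dose and Visit 9 nearly coincide for completers. A last-dose anchor alone would leave the same overlap.

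**The two-date wording is minor. This largely stands.** The natural reading applies the 30 days to both dates, so an unlimited window is a strained reading. What is missing is a rule for which date governs when they differ, as they can for early stoppers, for whom Visit 9 is the early-termination visit.

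None of this supplies a cut or a flag at the first open-label dose.

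**Conclusion.** The gap is real but conditional: AEs recorded in this study that start after roll-over could be counted under a blinded arm. The ceiling is 30 of 199 days. Under the stated assumptions the excess in placebo incidence is at most about 4 percentage points (about one subject of 24) and falls with lower uptake, longer lag or incomplete capture. It is a cheap correction to a stated rule.

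A reader might infer more, and the documents do not support it:
- That open-label events will be counted. They can be; capture and timing are unknown.
- That the active-placebo contrast shrinks. Roll-over subjects from the active arms can add open-label events too, so the net direction depends on uptake and hazards by arm, which are not given.
- That the bias is the full rise from 30% to 38%. About half of that rise is ordinary follow-up.
- That events are tabulated by randomised arm. SAP 5.2 uses treatment received, which coincides unless there was a dispensing error.

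**What to change.** In SAP 4.3.6, define a TEAE as an AE with onset from first dose to 30 days after the last dose of ATI-501 or placebo. This is a single anchor that matches Protocol 8.3.1. Then:
- exclude from the main by-arm TEAE tables any event with onset on or after the first open-label ATI-502 dose;
- tabulate those events separately, by original arm;
- add a supportive TEAE table that keeps the full 30-day window.

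The SAP should also say which database supplies AEs that start after roll-over.

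**Cost.** A short SAP edit, two added displays, and one first-dose date per roll-over subject from ATI-502-AA-203. The real downside is that roll-over subjects lose up to 30 days of post-treatment follow-up from the main table, so its follow-up length depends on roll-over and a late effect of oral ATI-501 could drop out of it. The separate and supportive tables are there to keep such events visible. AE collection and reporting periods do not change.

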### Treatment-emergent Laboratory Abnormalities

A treatment-emergent laboratory abnormality is defined as a result in which the baseline value is within normal laboratory limits and the post-baseline value is outside normal laboratory limits. If the relevant baseline assessment is missing, then any post-baseline value outside normal laboratory limits is treatment-emergent.

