**Table 2: Study Medication Interruption Criteria**

Laboratory Test	Hold Study Medication if:	Resume Study Medication if:
WBC count	< 2 x 10  /μL	≥ 2.5 x 10  /μL
ANC	< 1 x 10  /μL	≥ 1.5 x 10  /μL
Lymphocyte count	< 0.5 x 10  /μL	≥ 0.75 x 10  /μL
Platelet count	< 75 x 10  /μL	Returns to Baseline values
Hemoglobin	< 8 g/dL or a decrease > 2g/dL	≥ 10 g/dL
AST or ALT	> 3 x ULN	< 2 x ULN or within 20% of Baseline values
Serum creatinine	>2 x ULN	<1.5 x ULN or within 10% of Baseline value

Subjects with one or more of the Screening (Visit 1) laboratory values meeting the Study Medication Interruption Criteria found in [Table 2](#) must have repeat lab testing performed with results meeting the minimum criteria for resumption in order to initiate treatment at Baseline (Visit 2).

During treatment, if a subject has one or more of the abnormal laboratory values noted in [Table 2](#), the investigator or designee upon receipt and review of the central laboratory report should instruct the subject to hold study medication dosing. The investigator or designee should ask the subject about symptoms, concomitant illnesses and medications and repeat the test(s) as soon as possible. The Medical Monitor must be notified of dose interruptions due to SAEs considered related to study medication or laboratory abnormalities noted in [Table 2](#).

If the retest confirms the abnormal laboratory value, then the study medication should continue to be held followed by repeat testing once a week or sooner at the discretion of the investigator. The subject should be followed until the laboratory abnormality(s) returns to normal or to Baseline values.

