9. Evidence of active or latent bacterial (including tuberculosis) or viral infections at the time of enrollment, or history of incompletely treated or untreated tuberculosis. Subjects who have completed therapy for latent tuberculosis may participate. Refer to Exclusion Criterion 12 for herpes zoster, herpes simplex, or cytomegalovirus infections.
10. History of serious local infection (*e.g.*, cellulitis, abscess) or systemic infection including but not limited to a history of treated infection (*e.g.*, pneumonia, septicemia) within 3 months prior to Baseline. Subjects on an antibiotic for a nonserious, acute local infection must complete the course prior to enrollment into the study.
11. Positive for HIV, Hepatitis B or C. Subjects with serologic evidence of Hepatitis B vaccination (HepB surface Ab without the presence of Hep B surface Ag) will be allowed to participate.

12. History of recurrent herpes zoster (more than one episode) or disseminated herpes zoster (a single episode) or disseminated herpes simplex (single episode) or cytomegalovirus (CMV) that resolved less than 2 months before study enrollment. Subjects with a history of frequent outbreaks of Herpes Simplex Virus (defined as 4 or more outbreaks a year).
13. Clinically significant laboratory abnormalities at screening that, in the opinion of the Investigator, would make the subject a poor candidate for the study. [Subjects with any Screening laboratory values meeting the Study Medication Interruption Criteria found in [Table 2](#) must have repeat lab testing performed with results meeting the minimum criteria for resumption in order to initiate treatment at Baseline (Visit 2)].
14. Subjects with absolute neutrophil count  $<1,800/\mu\text{L}$ , or platelet count  $<130,000/\mu\text{L}$ .
15. Subjects who have received any of the following treatments for the timeframes specified below:
  - Disease Modifying Anti-Rheumatic Drugs (DMARDs), Biologics or immunosuppressants, including but not limited to: anakinra, adalimumab, azathioprine, corticosteroids, cyclosporine, etanercept, infliximab, methotrexate, TNF inhibitors, ustekinumab within 1 month or 5 half-lives (whichever is greater) of Baseline (Visit 2).
  - Plaquenil within 2 months of Baseline (Visit 2).
  - JAK inhibitors (oral or topical) within 6 months of Baseline (Visit 2).
  - Intralesional steroids or platelet rich plasma injections in the scalp within 1 month of Baseline (Visit 2).

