## 9.5. Safety Analyses

Safety analyses will include descriptive statistics calculated on the safety parameters using the safety population. The proportion of subjects with treatment-emergent adverse events will be

tabulated and presented by treatment and Medical Dictionary for Regulatory Activities (MedDRA) System Organ Class. Vital signs and clinically significant abnormal laboratory results will also be tabulated and presented by treatment group.

Data from all randomized subjects will be presented and summarized. Safety summaries by study treatment group will include listings by study medication of adverse events incidences within each MedDRA System Organ Class, and changes from pre-dose values in vital signs. Adverse event summaries will be presented by study medication showing the proportion of subjects experiencing adverse events, both overall and by MedDRA System Organ Class.

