### **6.3.2. Clinical Laboratory Assessments, Vital Signs, and Physical Examination Findings**

Descriptive summaries of quantitative clinical laboratory results (hematology, chemistry, and urinalysis) and their change from baseline values will be presented by study visit and treatment group. Observed values of categorical urinalysis data will be displayed with frequencies and percentages. All laboratory data will be listed for individual subjects.

Treatment-emergent abnormal laboratory assessments will be based on the lab-provided normal ranges. If the baseline laboratory assessment is normal and shifts to Low or High post-baseline,

then the laboratory value is considered a TE abnormal laboratory value. For each protocol specified lab test, the number and percent of subjects reporting a TE abnormal lab will be reported.

All laboratory summaries will be limited to the tests specified in the protocol.

Descriptive summaries of vital signs and their change from baseline will be presented by study visit and treatment group and all vital signs will be listed.

Post-baseline PE findings will be listed.

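### The SAP omits the by-arm table of clinically significant laboratory results that the protocol promises, and its treatment-emergent laboratory tables cannot count worsening from an abnormal baseline

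*SAP*

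**What the plan says.** **Clinically significant results.** Protocol 9.5, like the Synopsis, says that vital signs and "clinically significant abnormal laboratory results will also be tabulated and presented by treatment group". Protocol 8.1.5 requires the investigator to mark each out-of-range result as clinically significant (CS) or not (NCS).

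For laboratory data, SAP 6.3.2 plans by-visit descriptive summaries, frequencies for categorical urinalysis, counts of treatment-emergent abnormal results, and listings. SAP section 9 turns this into six tables: a summary table and a treatment-emergent table each for hematology, chemistry and urinalysis. None concerns clinical significance. SAP section 7 declares no departure from the protocol's analyses.

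**Treatment-emergent results.** SAP 4.3.6 requires that "the baseline value is within normal laboratory limits and the post-baseline value is outside normal laboratory limits". SAP 6.3.2 repeats the condition: "If the baseline laboratory assessment is normal and shifts to Low or High post-baseline". The one exception is in 4.3.6: "If the relevant baseline assessment is missing, then any post-baseline value outside normal laboratory limits is treatment-emergent". Baseline is "the last non-missing value obtained prior to initiation of study medication". Neither section has a rule for a subject whose baseline is already out of range.

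**The concern.** Safety and tolerability are part of the primary objective, and protocol Table 2 and section 3.4.1.2 interrupt or stop dosing on laboratory values. A reader comparing arms will turn first to the laboratory abnormality tables. Under the SAP rule those tables have three weaknesses.

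- A known abnormal baseline bars a subject from being counted for that test, whatever happens later. A missing baseline lets any abnormal value count.
- Severity plays no part, so a trivial crossing of the limit counts and a large deterioration may not.
- Subjects who cannot be counted remain in the denominator by default, which lowers the reported percentage.

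The protocol's CS table would partly offset this, because it does not depend on a normal baseline. It is the table that the SAP leaves out.

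**Working it through.** The plan states no figure on this point, so there is none to reproduce. The check compares the documents and then applies the SAP rule to cases set against the protocol's own limits.

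**1. Promised and planned tables.** The protocol promises CS laboratory results by arm. SAP tables 14.3.4.1.1 to 14.3.4.3.2 contain value and change summaries and treatment-emergent abnormal results. Listing 26 covers laboratory abnormalities but is a listing. The SAP does plan CS/NCS summaries for ECG (6.3.3) and for the baseline physical examination (6.1), but not for laboratory tests.

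**2. Can a subject enter out of range?** Yes.

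- Exclusion 13 covers "Clinically significant laboratory abnormalities at screening that, in the opinion of the Investigator, would make the subject a poor candidate for the study". It turns on judgement, not on the normal range.
- Table 2 forces a repeat test only when a screening value meets a hold limit, which for AST or ALT is above 3 x ULN. The AST/ALT level for starting treatment after a repeat is "< 2 x ULN or within 20% of Baseline values". For creatinine it includes values below 1.5 x ULN. Both allow values above ULN.
- Fixed numeric exclusions exist only for neutrophils (below 1,800/µL) and platelets (below 130,000/µL). The documents give no laboratory ranges, so it cannot be told whether those two limits lie below normal.

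**3. The rule applied.** A result is treatment-emergent if baseline is in range and the later value is out of range, or if baseline is missing and the later value is out of range.

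| Test | Baseline | Later value | Protocol level passed | Counted? |
|---|---|---|---|---|
| ALT | 0.9 x ULN | 1.05 x ULN | none | yes |
| ALT | 1.5 x ULN | 5.5 x ULN | 3 x ULN (Table 2), 5 x ULN (3.4.1.2) | no |
| ALT | 2.9 x ULN | 5.5 x ULN | same | no |
| Creatinine | 1.4 x ULN | 2.1 x ULN | 2 x ULN (both) | no |
| Hemoglobin | 10.5 g/dL | 6.4 g/dL | 8 g/dL (Table 2), 6.5 g/dL (3.4.1.2) | no, for assumed lower limits of normal from 11.5 to 13 |
| Lymphocytes | 0.75 x 10³/µL | 0.29 x 10³/µL | 0.5 x 10³/µL (Table 2) | no, for assumed lower limits of normal from 0.8 to 1.2 |
| ALT | missing | 5.5 x ULN | 3 and 5 x ULN | yes |
| Any | Low | High | – | no |

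Several section 3.4.1.2 limits also need persistence, a second event or a confirming retest. The table therefore shows the level reached, not that discontinuation was triggered.

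**4. Denominator.** SAP section 6 uses all subjects in the treatment group unless a table says otherwise, or those with a value at the visit for by-visit data. In both cases subjects with an abnormal baseline stay in.

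**5. Size.** The documents give no baseline abnormality rate. Purely as an assumption, let 5% to 30% of subjects be out of range at baseline on a given test. With 95/4 = 23.75 subjects per arm, 23.75 x 0.05 = 1.2 to 23.75 x 0.30 = 7.1 per arm could not be counted for that test. This is the number barred from counting. It is not the number who worsen, and it includes trivial baseline abnormalities.

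**The case against.** The best defence is that such a subject is missed by three tables, not by the safety report.

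- Protocol 8.1.5 makes a CS laboratory result after first dose an adverse event, and the adverse event definition includes deterioration of an existing condition. These events enter the TEAE tables by arm.
- A subject who meets a section 3.4.1.2 criterion must stop study medication permanently. Reasons for early termination (Table 14.1.1) and adverse events leading to discontinuation (Tables 14.3.1.6 and 14.3.1.7) are tabulated by arm.
- SAP section 6 includes minimum and maximum in descriptive statistics, so an extreme value or change would normally show in the by-visit summaries. All laboratory data are listed.
- The treatment-emergent rule is the same in both SAP sections, so it is a choice of summary in a Phase 2 trial and not an internal contradiction.

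All of this is right, and it rules out some readings that a reader might infer. The documents do not support saying that these subjects are counted nowhere, that by-visit summaries must hide them, or that the treatment-emergent tables are the only categorical laboratory output, since urinalysis frequencies are also planned.

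It does not close the gap. The adverse event route depends on the investigator's judgement, and protocol 8.2.1.1 prefers a diagnosis to a laboratory value where one is certain. By-visit extremes give no count of subjects. SAP 4.3.7 also summarizes only the result nearest the target day when a window holds several, so a severe unscheduled value can drop out. Listings are not comparisons by arm.

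**Conclusion.** Two points stand. The first is a plain mismatch: the protocol promises a by-arm CS laboratory table, the SAP has none, and SAP section 7 declares full consistency. This needs no assumption. Because CS/NCS summaries are planned for ECG and physical examination, it looks like an oversight, although the documents do not give the reason.

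The second is a rule that, followed exactly, gives a misleading count in Tables 14.3.4.1.2, 14.3.4.2.2 and 14.3.4.3.2. Those tables leave out worsening from an abnormal baseline, even to a hold or discontinuation level, and leave out reversals between Low and High. The subjects concerned stay in the default denominator.

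The number affected cannot be stated. A reader might take the 1.2 to 7.1 per arm above as subjects whose deterioration is missed. The documents do not support that: the rate is assumed, and harm needs both an abnormal baseline and later worsening. Nor do they show that the barred subjects are those at highest risk. The point merits correction before unblinding, chiefly because the remedy is cheap.

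**What to change.** 1. Add to SAP 6.3.2 and section 9 a table by arm of CS abnormal laboratory results, as protocol 9.5 promises. If the sponsor decides against it, SAP section 7 should declare the departure.
2. In SAP 4.3.6 and 6.3.2, also count Low-to-High and High-to-Low shifts as treatment-emergent. Add a baseline-to-worst-post-baseline shift table for each test. With only Low, Normal and High, a rise within High stays in one cell, so pre-specify bands inside those categories, for example at levels the protocol already uses.
3. Add a separate table, outside the treatment-emergent definition, of subjects by arm with any post-baseline value, scheduled or unscheduled, that meets each existing Table 2 or section 3.4.1.2 laboratory limit. Split it by whether the limit was already met at baseline, so that an unchanged value is not presented as emergent.

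Two details need settling before item 3 is programmed. Table 2 does not say from which value the hemoglobin decrease is measured. As printed, section 3.4.1.2 gives its two lymphocyte limits in different units, which must be reconciled.

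No clinical threshold changes. The cost is SAP wording and a few tables from data that the protocol already has sites collect. The sponsor should confirm that the CS/NCS classification of laboratory results is in the database, since protocol 8.1.5 does not say that it is entered in the eCRF.
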